2. INTRODUCTION

This SAP provides the detailed methodology for summary and statistical analyses of the data collected in study B9991024. This document may modify the plans outlined in the protocol; however, any major modifications of the primary endpoint definition or its analysis will also be reflected in a protocol amendment.

Statistical analyses will be performed using cleaned eCRF data as well as non-CRF data (ie, pharmacokinetics/pharmacodynamics and tumor assessment results by the Blinded Independent Central Review (BICR)). The primary analysis will include all data up to a clinical cut-off date corresponding to 18 months (78 weeks) after the last patient is treated. The final analysis of the data will be performed after last patient last visit (LPLV).

Additional analyses of the data may be performed for publication or regulatory reporting purposes.

2.1. Study Objectives

Primary Objectives

- To evaluate the safety and tolerability of avelumab in combination with axitinib as first line treatment in patients with advanced hepatocellular carcinoma (HCC).

Secondary Objectives

- To evaluate antitumor effect of avelumab in combination with axitinib as first line treatment in patients with advanced HCC per Response Evaluation Criteria in Solid Tumors (RECIST) v.1.1;
- To evaluate the OS of avelumab in combination with axitinib in patients with advanced HCC;
- To evaluate the pharmacokinetics of avelumab and axitinib when administered in combination;
- To evaluate candidate predictive biomarkers in pre-treatment tumor tissue that may aid in the identification of a patient subpopulation most likely to benefit from treatment with avelumab in combination with axitinib;
- To assess the immunogenicity of avelumab when combined with axitinib.

CCI

2.2. Study Design

This is an open-label, multi-center, single arm, Phase 1b study to evaluate the safety, efficacy and pharmacokinetics (PK) of avelumab in combination with axitinib as first line treatment in patients with advanced HCC.

Approximately 20 patients with advanced HCC who have not had prior systemic therapy will be enrolled in this study. The overall safety profile of these patients will be assessed after a minimum follow up of 3 months (ie, at least 3 months from last patient first dosing [LPFD]). Significant toxicities including immune-related adverse events (irAEs) which occur after 3 month follow up will also be included in the assessment.

Patients will receive avelumab 10 mg/kg every 2 weeks (Q2W) in combination with axitinib 5 mg twice a day (BID). If this dose level for the combination is not tolerable, a lower dose of the combination (avelumab 10 mg/kg IV Q2W plus axitinib 3 mg BID) may be evaluated with adding new cohort of patients. A cohort of patients aimed to evaluate avelumab 800 mg flat dose Q2W in combination with axitinib 5 mg BID may be added after the tolerability of avelumab 10 mg/kg Q2W in combination with axitinib 5 mg BID is confirmed.

Treatment with study drugs may continue until confirmed disease progression, patient refusal, patient lost to follow up, unacceptable toxicity, or the study is terminated by the sponsor, whichever comes first.

Patients who develop disease progression on study treatment but are otherwise continuing to derive clinical benefit from study treatment will be eligible to continue with avelumab combined with axitinib, single-agent avelumab, or single-agent axitinib provided that the treating physician has determined that the benefit/risk for doing so is favorable.

3. ENDPOINTS AND BASELINE VARIABLES: DEFINITIONS AND CONVENTIONS

3.1. Primary Endpoints

- Adverse events (AEs) and laboratory abnormalities as graded by National Cancer Institute (NCI) Common Terminology Criteria for Adverse Events (CTCAE) v.4.03.

AEs will be graded by the investigator according to the CTCAE v.4.03 and coded using the Medical Dictionary for Regulatory Activities (MedDRA).

Laboratory abnormalities as characterized by type, severity (as graded by NCI-CTCAE v.4.03) and timing.

3.2. Secondary Endpoints

3.2.1. Efficacy Endpoints

- Time to Progression (TTP), Progression Free Survival (PFS), Objective Response (OR), Disease Control (DC), Time to Tumor Response (TTR) and Duration of Response (DR), per RECIST v.1.1;

TTP is defined as the time from the date of first dose of study treatment to the date of the first documentation of objective progression of disease (PD).

PFS is defined as the time from the date of first dose of study treatment to the date of the first documentation of PD or death due to any cause, whichever occurs first.

OR is defined as complete response (CR) or partial response (PR) according to RECIST v1.1 from the date of first dose of study treatment until the date of the first documentation of PD. Both CR and PR must be confirmed by repeat assessments performed no less than 4 weeks after the criteria for response are first met.

DC is defined as CR, PR, non-CR/non-PD or SD. Both CR and PR must be confirmed by repeat assessments performed no less than 4 weeks after the criteria for response are first met. Criteria for SD and non-CR/non-PD must have been met at least 8 weeks after date of first dose of study treatment.

TTR is defined, for patients with an OR, as the time from the date of first dose of study treatment to the first documentation of objective response (CR or PR) which is subsequently confirmed.

DR is defined, for patients with an OR, as the time from the first documentation of objective response (CR or PR) to the date of first documentation of PD or death due to any cause.

- Overall Survival (OS).

OS is defined as the time from the date of first dose of study treatment to the date of death due to any cause.

3.2.2. Pharmacokinetic Endpoints

- PK parameters including trough and maximum concentrations (C_{trough} , C_{max}) of avelumab and axitinib.

These parameters will be calculated at Cycles 2, 3, 4, 6, 8, then every 4 cycles for avelumab and at Cycles 2, 3 for axitinib.

Table 2. PK Parameters to be Determined for Avelumab and axitinib

Parameter	Definition	Method of Determination
C_{max}	Maximum observed concentration	Observed directly from data
C_{trough}	Predose concentration during multiple dosing	Observed directly from data

3.2.3. Immunogenicity Endpoints

- Anti-drug antibodies (ADAs, neutralizing antibodies [nAbs]) for avelumab when in combination with axitinib.

These endpoints at Cycles 2, 3, 4, 6, 8, then every 4 cycles, end of treatment/withdrawal and 30 days after end of avelumab treatment regardless of continuation of axitinib therapy will be evaluated.

3.2.4. Biomarker Endpoints

- Tumor tissue biomarker status (ie, positive or negative based on, for example, PD-L1 expression and/or quantitation of tumor infiltrating CD8+ T lymphocytes as assessed by immunohistochemistry [IHC]).

Table 3. Biomarker Definition and Determination

Parameter	Definition	Method of Determination
PD-L1 expression	The number of PD-L1 positive cells and/or qualitative assessment of PD-L1 staining on tumor and inflammatory cells in regions of interest that are defined by tumor cell morphology and the presence or absence of CD8+ cells	Pathologist, assisted by image analysis
Tumor infiltrating CD8+ lymphocytes	The number of CD8+ cells per unit area and the percent of counted cells that are scored as CD8+	Pathologist, assisted by image analysis

CCI

3.4. Baseline Variables

3.4.1. Study Drug, Study Treatment and Baseline Definitions

In this study, ‘study drug’ refers to avelumab or axitinib and ‘study treatment’ (or ‘treatment group’) refers to the following:

- avelumab 10 mg/kg in combination with axitinib 5 mg.

If avelumab 10 mg/kg in combination with axitinib 5 mg is not tolerable, a lower dose of the combination may be added as another treatment group evaluated in a new cohort of patients.

Start and end dates of study treatment:

The date/time of first dose of study treatment in a combination group is the earliest date/time of the first non-zero dose date/time for the study drugs in the combination.

The date/time of last dose of study treatment in a combination group is the latest date/time of the last non-zero dose date/time for the study drugs in the combination.

Definition of baseline:

The last available assessment prior to the start of study treatment is defined as ‘baseline’ value or ‘baseline’ assessment for safety, biomarker and efficacy analyses. If an assessment is planned to be performed prior to the first dose of study treatment in the protocol and the assessment is performed on the same day as the first dose of study treatment, it will be assumed that it was performed prior to study treatment administration, if assessment time point is not collected or is missing. If assessment time points are collected, the observed time

point will be used to determine pre-dose on study Day 1 for baseline calculation. Unscheduled assessments will be used in the determination of baseline. However, if time is missing, an unscheduled assessment on study Day 1 will be considered to have been obtained after study treatment administration.

Patients who start treatment and discontinue from the study on the same day may have two different sets of data collected on study Day 1 (one during study and one in the End of Treatment (EOT)) visit. Data reported at the EOT visit are not eligible for baseline selection.

If a scheduled pre-dose measurement actually occurred post-dose, then the corresponding measurement will be treated and analyzed similar to an unscheduled post-dose measurement.

Baseline for RR and QT/QTc interval assessments will be derived from the visit where both RR and QT are not missing. Triplicate ECGs are collected in the study and the baseline for each ECG measurement is the average of the pre-dose replicate measurements on the baseline day. Unscheduled assessments will not be included in the calculation of the average. QTcB and QTcF will be derived based on RR and QT. The average of the replicate measurements will be determined after the derivation of the individual parameter at each time point.

Replicate vital signs are collected in the study and the baseline for each vital sign parameter is the average of the pre-dose replicate measurements on the baseline day. Unscheduled assessments will not be included in the calculation of the average.

3.4.2. Baseline Characteristics

Baseline characteristics (including demographics, physical measurements, disease history and prior anti-cancer therapies) are described in [Section 6.5.1](#). These baseline characteristics are not planned to be included as stratification variables or covariates in statistical models unless otherwise specified in [Section 6](#).

3.5. Safety Endpoints

3.5.1. Adverse Events

Treatment-Emergent Adverse Events

Treatment-emergent adverse events (TEAEs) are those events with onset dates occurring during the on-treatment period for the first time, or if the worsening of an event is during the on-treatment period.

On-treatment period is defined as the time from the first dose of study treatment through minimum (30 days + last dose of study treatment, start day of new anti-cancer drug therapy – 1 day). The start day of new anti-cancer drug therapy after the first dose of study treatment is derived as outlined in [Section 5.2.5](#).

Adverse Events of Special Interest (AESIs)

AESIs are irAE and infusion-related reactions (IRRs). The criteria for classification of an AE as an irAE or IRR are described in [Appendix 1](#) and [Appendix 2](#), respectively.

4. ANALYSIS SETS

Data for all patients will be assessed to determine if patients meet the criteria for inclusion in each analysis population prior to releasing the database and classifications will be documented per Pfizer's standard operating procedures.

Only patients who signed informed consent will be included in the analysis sets below.

4.1. Full Analysis Set

The full analysis set (FAS) will include all patients who receive at least one dose of study drug. Patients will be classified according to the study treatment actually received. If a patient receives more than one treatment the patient will be classified according to the first study treatment received.

4.2. Safety Analysis Set

The safety analysis set will include all patients who receive at least one dose of study drug. Patients will be classified according to the study treatment actually received. If a patient receives more than one study treatment, the patient will be classified according to the first study treatment received. In this non-randomized study, the FAS and the safety analysis set are identical.

4.3. Other Analysis Set

4.3.1. PK Analysis Set

The PK concentration analysis set is a subset of the safety analysis set and will include patients who have at least one post-dose concentration measurement above the lower limit of quantitation (LLQ) for avelumab or axitinib.

The PK parameter analysis set is a subset of the safety analysis set and will include patients who have at least one of the PK parameters of interest for avelumab or axitinib.

4.3.2. Biomarker Analysis Set

The biomarker analysis set for biomarkers that are measured only at screening is a subset of the safety analysis set and will include patients who have at least one screening biomarker assessment.

The biomarker analysis set for biomarkers that are measured sequentially is a subset of the safety analysis set and will include patients who have at least one baseline and one on treatment biomarker assessment for the same marker.

Analysis sets will be defined separately for blood-based and tumor tissue-based biomarkers.

4.3.3. Immunogenicity Analysis Set

The immunogenicity analysis set is a subset of the safety analysis set and will include patients who have at least one ADA/nAb sample collected for avelumab.

5. GENERAL METHODOLOGY AND CONVENTIONS

5.1. Hypotheses and Decision Rules

5.1.1. Hypotheses and Sample Size Determination

There is no formal hypothesis testing planned for this study.

This study will enroll 20 patients to evaluate overall safety and tolerability with combination of avelumab plus axitinib. A sample size of 20 patients will provide at least 88% probability to observe at least one AE if the true incidence of the AE in the population is 10% or more.

5.1.2. Decision Rules

Not applicable.

5.2. General Methods

As described in [Section 3.4](#), in this study ‘**treatment group**’ refers to the following:

- avelumab 10 mg/kg in combination with axitinib 5 mg.

If avelumab 10 mg/kg in combination with axitinib 5 mg is not tolerable, a lower dose of the combination may be added as another treatment group evaluated in a new cohort of patients.

Baseline characteristics, disposition and efficacy data will be summarized based on the FAS by treatment group.

Safety data, exposure data, concomitant medications and non-drug treatments will be summarized based on the safety analysis set by treatment group.

PK data will be summarized based on the PK analysis set by treatment group.

Biomarker data will be summarized based on the biomarker analysis set by treatment group.

Immunogenicity data will be summarized based on the immunogenicity analysis set by treatment group.

5.2.1. Data Handling after the Cut-off Date

Data after the cut-off date may not undergo the cleaning process and will not be displayed in any listings or used for summary statistics, statistical analyses or imputations.

5.2.2. Pooling of Centers

In order to provide overall estimates of treatment effects, data will be pooled across centers. The ‘center’ factor will not be considered in statistical models or for subgroup analyses due to the high number of participating centers in contrast to the anticipated small number of patients treated at each center.

5.2.3. Presentation of Continuous and Qualitative Variables

Continuous variables will be summarized using descriptive statistics ie, number of non-missing values and number of missing values [ie, n (missing)], mean, median, standard deviation (SD), minimum, maximum and first and third quartile (Q1 and Q3).

Qualitative variables will be summarized by frequency counts and percentages. Unless otherwise specified, the calculation of proportions will include the missing category. Therefore, counts of missing observations will be included in the denominator and presented as a separate category.

In case the analysis refers only to certain visits, percentages will be based on the number of patients still present in the study at that visit, unless otherwise specified.

5.2.4. Definition of Study Day

Start day of study treatment is the day of the first dose of study treatment.

The study day for assessments occurring on or after the start of study treatment (eg, adverse event onset, tumor measurement) will be calculated as:

$$\text{Study day} = \text{Date of the assessment/event} - \text{start of study treatment} + 1.$$

The study day for assessments occurring prior to the first dose of study treatment (eg, baseline characteristics, medical history) will be negative and calculated as:

$$\text{Study day} = \text{Date of the assessment/event} - \text{start of study treatment}.$$

The study day will be displayed in all relevant data listings.

5.2.5. Definition of Start of New Anti-cancer Drug Therapy

Start date of new anti-cancer drug therapy is used to determine the end of the on-treatment period (see [Section 5.2.7](#)).

The start date of new anti-cancer drug therapy is the earliest start date of anti-cancer drug therapy recorded in the 'Follow-up Cancer Therapy' eCRF pages that is after the first dose of study treatment. When start date of anti-cancer drug therapy is missing or partially missing, the imputation rules described in [Section 5.3.3.4](#) should be applied using only data from the 'Follow-up Cancer Therapy' eCRF pages.

5.2.6. Definition of Start of New Anti-cancer Therapy

Start date of new anti-cancer therapy (drug, non-drug locoregional, radiation, surgery) is used for censoring in efficacy analyses (see [Section 6.2.1](#)).

The start date of new anti-cancer therapy is the earliest date after the first dose of study treatment amongst the following:

- Start date of anti-cancer drug therapy recorded in the 'Follow-up Cancer Therapy' eCRF pages;

- Start date of anti-cancer non-drug locoregional therapy recorded in the eCRF pages related to the follow-up non-drug locoregional treatments;
- Start date of radiation therapy recorded in ‘Concomitant Radiation Therapy’, and ‘Follow-up Radiation Therapy’ eCRF pages with ‘Treatment Intent’ = ‘Curative in intent’;
- Surgery date recorded in ‘Concomitant Surgery’, and ‘Follow-up Surgery’ eCRF pages when ‘Surgery Outcome’ = ‘Resected’ or ‘Partially Resected’.

When start date of anti-cancer therapy is missing or partially missing, the imputation rules described in [Section 5.3.3.4](#) should be applied using ‘Follow-up Cancer Therapy’ eCRF page, eCRF pages related to the follow-up non-drug locoregional treatments, ‘Concomitant Radiation Therapy’, ‘Follow-up Radiation Therapy’, ‘Concomitant Surgery’, and ‘Follow-up Surgery’ eCRF pages.

5.2.7. Definition of On-treatment Period

Safety endpoints will be summarized based on the on-treatment period unless otherwise specified.

On-treatment period is defined as the time from the first dose of study treatment through minimum (30 days + last dose of study treatment, start day of new anti-cancer drug therapy – 1 day).

Safety data collected outside the on-treatment period as described above will be listed and flagged in listings but not summarized.

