8.1.4. Time Period for Collecting AE/SAE Information

The time period for actively eliciting and collecting AEs and SAEs (“active collection period”) for each patient begins from the time the patient provides informed consent, which is obtained before the patient’s participation in the study (ie, before undergoing any study-related procedure and/or receiving investigational product), through and including a minimum of 90 calendar days after the last administration of investigational product.

For patients who are screen failures, the active collection period ends when screen failure status is determined.

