8.1.4.2. Recording Non-serious AEs and SAEs on the CRF

During the active collection period, both non-serious AEs and SAEs are recorded on the CRF.

Follow-up by the investigator may be required until the event or its sequelae resolve or stabilize at a level acceptable to the investigator, and Pfizer concurs with that assessment.

If a patient begins a new anticancer therapy, the recording period for non-serious AEs ends at the time the new treatment is started; however, SAEs must continue to be recorded on the CRF during the above-indicated active collection period.

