6.6.1. Adverse Events

Treatment-emergent adverse events (TEAEs) are those events with onset dates occurring during the on-treatment period for the first time, or if the worsening of an event is during the on-treatment period as defined in [Section 3.5.1](#).

All analyses described will be based on TEAEs (started during the on-treatment period) if not otherwise specified. The AE listings will include all AEs (whether treatment-emergent or not). AEs outside the on-treatment period will be flagged in the listings.

- **Related Adverse Events:** adverse events with relationship to study treatment (as recorded on the AE eCRF page, Relationship with study treatment = Related) reported by the investigator and those of unknown relationship (ie, no answer to the question ‘Relationship with study treatment’). Related AEs are those related to any study drug (ie, at least one of the study drugs).
- **Serious Adverse Events (SAE):** serious adverse events (as recorded on the AE eCRF page, Serious Adverse Event = Yes).

- **Adverse Events Leading to Dose Reduction:** adverse events leading to dose reduction of study treatment (as recorded on the AE eCRF page, Action taken with study treatment = Drug reduced).
- **Adverse Events Leading to Interruption of Study Treatment:** adverse events leading to dose interruption of study treatment (as recorded on the AE eCRF page, Action taken with study treatment = Drug interrupted). The eCRF does not allow for a clear separation between interruption of an infusion and delays of administration for a parenteral drug as both are recorded using the same term on the eCRF (“Drug interrupted”). IRRs will be excluded in the analysis of AEs leading to Drug Interruption in case they only led to an interruption of the infusion.
- **Adverse Events Leading to Permanent Treatment Discontinuation:** adverse events leading to permanent discontinuation of study treatment (as recorded on the AE eCRF page, Action taken with study treatment = Drug withdrawn).
- **Adverse Events Leading to Death:** adverse event leading to death (as recorded on the AE eCRF page, Outcome = Fatal, as well as AEs of Grade 5).
- **Immune-related Adverse Events (irAE):** irAEs (as identified according to the methodology outlined in [Appendix 1](#) for a pre-specified search list of MedDRA PTs, documented in the Safety Review Plan and finalized for analysis of the current studies data prior to DB lock).

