6.6.3. Serious Adverse Events

The frequency (number and percentage) of patients with each of the following will be presented for treatment-emergent SAEs by treatment group:

- SAEs by SOC and PT;
- Related SAEs by SOC and PT.

The listings of all SAEs will also be provided with the relevant information with a flag for SAEs with onset outside of the on-treatment period.

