9. APPENDICES

Appendix 1. Immune-Related Adverse Events

The MedDRA PTs and clusters for irAEs are defined in the Safety Review Plan (SRP) for avelumab.

Immune-related AEs (irAEs) will be programmatically identified as outlined in Table 11. This case definition is hierarchical, ie, each step is only checked for patients and events that have already met the prior step.

Table 11. Case Definition for irAEs

Step	Selection Criteria	Additional Notes
1	Event selected based on a list of pre-specified MedDRA PTs within clusters. These are included in the SRP as Tier1 events (Immune-mediated xxxx). If AE matches the list then it is in for the next step	
2	AE onset during 1 st study drug administration or anytime thereafter through 90 days after last dose of study treatment	This is regardless of start of new anti-cancer drug therapy and regardless of TEAE classifications
3	Answer in the AE eCRF page to ‘Was another treatment given because of the occurrence of the event’ is ‘YES’	
4	AE treated with corticosteroids or other immunosuppressant therapy. For endocrinopathies only: AE required hormone replacement	Look in the conmed pages for AE identifiers that match the AEs from Step 3. For each of such AEs if A) OR B) OR C) below are met then the AE is in for the next step A) conmed ATC code is in (H02A, H02B, D07, A01AC, S01BA, S01BB, L04AA, L04AB, L04AC, L04AD, L04AX A07EA) and AE PT is in any of the irAE clusters. B) conmed ATC code is in (H03A, H03B) and AE PT is in one of the irAE clusters associated with “Immune-mediated endocrinopathies” C) conmed ATC code is A10A and AE PT is in the irAE cluster associated with “Immune-mediated endocrinopathies: Type I Diabetes Mellitus”

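### Serious and Grade ≥3 adverse events that are not classified as immune-related are collected to day 90 after last dose, but those starting after the 30-day on-treatment period are only listed, not tabulated

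*SAP*

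**What the plan says.** **Collection.** Protocol 8.1.4 has AEs and SAEs actively collected from consent "through and including a minimum of 90 calendar days after the last administration of investigational product". Under Protocol 8.1.4.2, recording of non-serious AEs stops when a new anticancer therapy starts, but "SAEs must continue to be recorded on the CRF during the above-indicated active collection period".

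**Default summary window.** SAP 5.2.7 states: "Safety endpoints will be summarized based on the on-treatment period unless otherwise specified". That period runs from first dose to "minimum (30 days + last dose of study treatment, start day of new anti-cancer drug therapy", less one day in the case of the new drug. For anything later: "Safety data collected outside the on-treatment period as described above will be listed and flagged in listings but not summarized".

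**Tables that follow the window.** SAP 6.6.1: "All analyses described will be based on TEAEs (started during the on-treatment period) if not otherwise specified". This governs the Grade ≥3 and leading-to-death tables in 6.6.1.1. In SAP 6.6.3 the SAE frequencies "will be presented for treatment-emergent SAEs by treatment group", and SAEs with later onset get a flag in the listing.

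**Tables that do not follow it.** SAP Appendix 1, Table 11, admits irAEs with onset during first study drug administration or "anytime thereafter through 90 days after last dose of study treatment", whether or not a new anti-cancer drug has started and whether or not the event is a TEAE. SAP 6.6.4 tabulates all, Grade ≥3, serious and fatal irAEs. SAP 6.6.2 tabulates all deaths by reason, with no time limit.

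SAP 6.1.1.1 defines the primary analysis as Sections 6.6.1 to 6.6.5, so both kinds of table belong to it.

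**The concern.** The trial's primary purpose is to describe the safety and tolerability of the combination. Sites must record SAEs for three months after treatment, yet the main SAE table stops after one month, or sooner after a change of drug. A late SAE or Grade ≥3 event that is not an irAE is collected, cleaned and listed, but adds nothing to any reported frequency. If such events occur in patients not already counted, the headline SAE and Grade ≥3 percentages will be lower than the collected data would give.

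There is also an internal inconsistency. The irAE tables run to day 90 and the SAE tables do not, so the same event can count in one and not in the other. The overall AE summary in SAP 6.6.1.1 sets an irAE row beside Grade ≥3, serious and fatal TEAE rows, which puts two windows in one table. The last sentence of SAP 5.2.7 does not mention the 90-day exception.

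**Working it through.** **1. The plan's own figure.** Protocol 9.1 and SAP 5.1.1 give at least 88% probability of seeing at least one AE in 20 patients when the true incidence is 10%. Check: 1 − 0.9^20 = 0.878. This agrees after rounding and is not in dispute.

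**2. Length of the gap.** Collection runs to day 90 after last dose and the default summary to day 30. Days 31 to 90 are 90 − 30 = 60 days, and 60/90 = 67% of the post-treatment collection period. These are days, not events. As an example, if a new drug starts on day 15, the window closes on day 14 and days 15 to 90 (76 of 90 days, 84%) are outside it. Because non-serious recording stops at new therapy anyway, that earlier cut mainly affects SAEs.

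**3. Where each kind of event goes.** Days are counted from last dose.

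| Event | Reaches a frequency table? |
|---|---|
| Serious irAE, onset day 60 | Yes, serious irAEs (6.6.4); no, SAEs (6.6.3) |
| Serious non-irAE, onset day 60 | No; flagged listing only |
| Non-serious Grade ≥3 non-irAE, onset day 60, no new therapy | No; flagged listing only |
| Non-serious Grade ≥3 non-irAE, onset after new therapy | Recording has stopped under Protocol 8.1.4.2 |
| Serious non-irAE, onset day 20, new drug from day 15 | No; flagged listing only |
| Fatal non-irAE, onset day 60 | Death counted by broad reason (6.6.2); no organ-class, preferred-term or relatedness table |
| AE with onset in the window, fatal later | Yes, TEAE leading to death, since TEAE status depends on onset or worsening in the window |

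**4. Sensitivity, by assumption only.** The documents give no rate of late events. Take a type of AE, not an irAE, with 10% incidence over the full collection period, and let f be the assumed share of affected patients whose only onset falls outside the window. The chance that it appears at all in a TEAE table is 1 − (1 − 0.10 × (1 − f))^20:

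| f | Incidence in window | Probability of appearing |
|---|---|---|
| 0% | 10% | 87.8% |
| 10% | 9% | 84.8% |
| 20% | 8% | 81.1% |
| 30% | 7% | 76.6% |
| 50% | 5% | 64.2% |

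A table over the full 90 days gives 87.8% whatever f is. With 20 patients, each one not counted is 1/20 = 5 percentage points.

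**The case against.** A 30-day treatment-emergent window is a legitimate analysis choice. Protocol 9.4.1.1 puts the emphasis on treatment-emergent events without fixing a day limit, and Protocol 9 lets the SAP modify the outlined plan. The late toxicity most expected of a checkpoint inhibitor already has a 90-day window. Appendix 1 also lets medical review add irAEs that the algorithm misses, so a late immune event managed without steroids need not be lost. Last dose means the later of the two drugs' last doses (SAP 3.4.1), so a patient who stays on axitinib alone remains in the window. Late events are listed, and in about 20 patients a flagged listing can be read. All of this stands, and it limits the point to events not classified as irAEs.

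Three stronger readings are tempting and are not supported:

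- **That late deaths are left out of the primary safety result.** They are not: SAP 6.6.2 counts all of them by reason, including treatment toxicity and unrelated AE.
- **That a number of missed patients can be stated.** An assumed SAE rate of 0.05 to 0.15 per patient per 30 days gives 20 × (1 − exp(−2 × 0.05)) = 1.9 to 20 × (1 − exp(−2 × 0.15)) = 5.2 patients with an SAE on days 31 to 90. The rate has no source in the documents. The sum also includes late irAEs and patients already counted for an earlier SAE, and assumes that all 20 are followed to day 90.
- **That the SAP contradicts the protocol.** Protocol 3 and SAP 2.2 promise to include significant toxicities, irAEs among them, that occur after three months of follow-up. That clock runs from the last patient's first dose, not from each patient's last dose. The wording shows that interest in late toxicity is not confined to irAEs, but it sets no tabulation window.

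One further objection bears on the remedy. Protocol 8.2.3 requires fatal progression in the collection period to be recorded as a Grade 5 SAE, so a plain 90-day table would mix toxicity with progression.

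**Conclusion.** The point holds for a defined set of events: SAEs and Grade ≥3 AEs that are not irAEs and start after the on-treatment period. They are collected to day 90 (non-serious ones only until new therapy) and are listed, not tabulated. For fatal events, only the organ-class, preferred-term and relatedness breakdown of late-onset non-irAEs is missing. The different window for irAEs makes the SAE and irAE tables inconsistent with each other.

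The size is known in days (60 of 90, more after an early change of drug) but not in patients. The table over f illustrates the sensitivity and does not estimate the loss. The effect on reported rates depends on how many patients have their only qualifying event outside the window, which the documents do not say. This is a cheap improvement, not the correction of an error in the 30-day definition.

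**What to change.** - Keep the 30-day TEAE tables unchanged.
- In SAP 6.6.1 and 6.6.3, add one supplementary table covering first dose through 90 days after last dose, for SAEs, Grade ≥3 AEs and AEs leading to death, by organ class, preferred term and relatedness.
- Show SAEs with onset after new anti-cancer therapy in a separate column.
- Put disease-progression events on a separate row. The new-therapy column alone will not isolate patients who progress and die without further treatment.
- In SAP 5.2.7, name this table and the 90-day irAE window as exceptions to the rule that later data are not summarised.

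The cost is SAP wording and one extra table, with no new data collection. The downside is that some late events will reflect progression or later therapy, which the separate row and column make visible but do not fully resolve.
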